3.3 Study Rationale

Combination therapy consisting of bavituximab and sorafenib is attractive for patients with advanced HCC for the following reasons:

1. Based on the previously mentioned SHARP trial, sorafenib is the first drug in the modern era to receive FDA approval for treatment of advanced HCC. Although sorafenib is now established as part of standard therapy, its overall benefit is modest, and advanced HCC remains uniformly fatal. Due to the multiple escape mechanisms for angiogenesis inhibition in HCC, a logical next step would be to combine sorafenib with other biologic or chemotherapeutic agents.
2. Externalized PS is a desirable marker for tumor targeting for several reasons: PS is specifically and abundantly expressed on tumor vascular endothelium; it is present on a high percentage of tumor endothelial cells in a variety of solid tumors; it is absent from non-tumor vasculature; and it is expressed on the luminal side of tumor vascular endothelium, which is readily accessible for targeting drugs. Combining bavituximab, an angiogenesis inhibitor, with sorafenib, an angiogenesis inhibitor with a different mechanism, may prevent signaling escape mechanisms seen with either drug if given individually.
3. Data from preclinical studies have demonstrated that sorafenib therapy increases PS exposure on tumor vascular endothelium in a HCC tumor model. The increase of PS exposure will amplify the target for bavituximab and should increase tumor vessel destruction producing increased treatment efficacy.

It is our hypothesis that combination therapy with bavituximab and sorafenib will provide greater clinical efficacy than either agent alone with minimal toxicity.

4.0 OVERVIEW OF STUDY DESIGN/INTERVENTION

4.1 Design

This is a non-randomized, open-label, single-institution phase I/II therapeutic trial of bavituximab and sorafenib in patients with advanced HCC. This study will be activated at the UT Southwestern Medical Center, (comprised of The Harold C. Simmons Comprehensive Cancer Center, UT Southwestern Hospitals-St. Paul and Parkland Memorial Hospital System), VA-North Texas, and UT Austin-Seton. Advanced HCC is defined as disease that is not amenable to surgical resection or orthotopic liver transplantation or is metastatic in nature.

The phase I component of the study will consist of a traditional 3+3 dose escalation rule as outlined in section 11.0.

[figure not shown]
The dose levels of bavituximab (0.3,1.0,and 3.0 mg/kg weekly) were selected based on available data from preclinical and clinical studies that is predicted to achieve and sustain biologically active blood antibody levels or tumor binding in cancer patients.

- A bavituximab dose of 3 mg/kg gives a blood concentration in excess of that needed for maximal efficacy based on preclinical models while having little effect on coagulation and safety laboratory parameters and causing no significant depletion of the cofactor protein, β 2GP1.
- In preclinical models, dosing above the biologically effective blood concentration of 2 μ g/mL did not increase anti-tumor efficacy.
- Treatment with \leq 3 mg/kg bavituximab appears to be well tolerated.
- β 2-glycoprotein I levels are significantly depleted above 3 mg/kg bavituximab.

4.2 Intervention

4.2.1 Phase I component

The following is a brief schematic of Phase I component study flow:

Patients will be eligible for enrollment on study if they have a diagnosis of HCC by at least one of the following criterion listed below:

- a. Histologically confirmed hepatocellular carcinoma
- b. Axial imaging consistent with liver cirrhosis and at least one solid liver lesion ≥ 2 cm with early enhancement and delayed enhancement washout regardless of alpha-fetoprotein (AFP) levels.
- c. AFP ≥ 400 ng/ml and evidence of at least one solid liver lesion ≥ 2 cm regardless of specific imaging characteristics.

[figure not shown]
Patients also need to have advanced disease as defined previously in section 4.1. Attending surgical oncology, hepatologists and liver transplant physicians (either surgeons or hepatologists) with expertise in the management of HCC will assess suitability of surgical resection and liver transplantation at participating sites.

All patients will initially be staged with a liver protocol MRI or CT of the abdomen. A chest CT will be done if there is a concern for intra-pulmonary metastases.

Bavituximab will be administered on a weekly schedule until completion of the phase I component of the study or the development of any of the criteria for requiring removal from the study as outlined in Section 11 of the protocol. Bavituximab will be dosed according to the timeline of the phase I and II components of the study. In the phase I component, bavituximab will be started at 0.3 mg/kg and will be escalated pending DLT to 1.0 mg/kg and 3.0 mg/kg. These doses will be given intravenously over 90 minutes starting on day 1. Sorafenib will be initially dosed at 200 mg orally twice a day and escalated to the target dose of 400 mg orally twice a day at the discretion of the treating medical oncologist. Sorafenib will be started within 3 days of the initial bavituximab

dose. At the completion of the study treatment period of one cycle sorafenib will be continued at the discretion of the treating oncologist.

4.2.2 Phase II Component

Patients will be eligible for enrollment on study if Histologically confirmed hepatocellular carcinoma.

Patients also need to have advanced disease as defined previously in section 4.1. Attending surgical oncology, hepatologists and liver transplant physicians (surgeons or hepatologists) with expertise in the management of HCC will assess suitability of surgical resection and liver transplantation at participating sites.

All patients will initially be staged with a liver protocol CT or MRI of the abdomen. A chest CT will be done if there is a concern for intra-pulmonary metastases.

Prior to the initiation of therapy serological markers (alpha-fetoprotein and viral hepatitis markers, including hepatitis C antibody and hepatitis B surface antigen), serum, image guided core biopsy of an intra-hepatic tumor (performed for clinical care. If the biopsy is performed for clinical care, additional needle core specimens (up to 3) will be obtained in addition to the number needed for

histopathological analysis. This is of minimal additional risk as same needle tract will be used to acquire additional specimens.

Bavituximab will be administered on a weekly schedule until intolerable toxicity, or the development of any of the criteria for requiring removal from the study as outlined in Section 14 of the protocol. Sorafenib will be administered on a daily schedule until intolerable toxicity, or the development of any of the criteria for requiring removal from the study as outlined in Section 14 of the protocol. The dose of bavituximab for the phase II component will be the maximum tolerated dose determined in the phase I component. In the phase I component, bavituximab will be started at 0.3 mg/kg and will be escalated pending DLT to 1.0 mg/kg and 3.0 mg/kg. These doses will be given intravenously over 90 minutes starting on day Sorafenib will be initially dosed at 200 mg orally twice a day and escalated to the target dose of 400 mg orally twice a day at the discretion of the treating medical oncologist. Sorafenib will be started within 3 days of the initial bavituximab dose.

Between five and six weeks following the first dose of bavituximab, alpha-fetoprotein(serum), a second image guided core biopsy of an intra-hepatic tumor will be performed.. This second image guided biopsy is optional and will be subject to informed consent with the enrolled patient. This biopsy will be for research purposes only and performed in the exact same way as the clinical care biopsy.

Bavituximab and sorafenib will be administered until intolerable toxicity, or the development of any of the criteria for requiring removal from the study as outlined in Section 14 of the protocol. Serum studies (including alfa-fetoprotein) and CT or MRI will be performed every 6 weeks +/- 5 days following the initial 2-week studies until removal from study. All patients will be followed long-term for the secondary endpoint, overall survival, to a point 12 months from accrual of the final patient.

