10.0 EVALUATION DURING TREATMENT/INTERVENTION

Investigations/Tests	Baseline	At Each Dose of Bavituximab	6 Weeks (+/-5 days) After Initiation of Therapy
Detailed history and physical examination (including height, weight, ECOG, vitals)	X	X (Day 1 of each cycle only)	
Written Informed Consent	X		X (for image guided biopsy)

			of tumor) (phase II only)
EKG	X		
Research Serum	X (phase II only)		X (and every 6 weeks thereafter) (phase II only)
Image-guided biopsy of tumor,	X (phase II only)		X (phase II only, between 5 and 6 weeks)
Hematology (CBC with differential)	X	X	
Liver function tests (including total bilirubin, AST, ALT)	X	X	
Coagulation tests (including PT, aPTT, INR)	X	X	
Urinalysis	X		
Alpha-fetoprotein	X	X	
MRI abdomen with gadolinium or CT Abdomen	X		X (and every 6 weeks thereafter) (phase II only)
Bilateral lower extremity venous duplex	X		X (phase II only)
Viral hepatitis titers (Hepatitis B and C)	X (phase II only)		

Investigations/tests at study exit due to disease progression or toxicity or following completion of the phase I component

- Bilateral venous duplex of lower extremities

- History and physical examination (this will continue every 6 weeks for determination of secondary endpoint of overall survival)
- Laboratory tests: same as required at baseline

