13.4 Evaluation of best overall response

The best overall response is the best response recorded from the start of the treatment until disease progression/recurrence (taking as reference for progressive disease the smallest measurements recorded since the treatment started). The patient's best response assignment will depend on the achievement of both measurement and confirmation criteria.

Target Lesions	Non-target lesions	New lesions	Overall response
CR	CR	No	CR
CR	Non-CR/Non-PD	No	PR
PR	Non-PD	No	PR
SD	Non-PD	No	SD
PD	Any	Yes or No	PD
Any	PD	Yes or No	PD
Any	Any	Yes	PD

1. Patients with a global deterioration of health status requiring discontinuation of treatment without objective evidence of disease progression at that time should be reported as "symptomatic deterioration". Every effort should be made to document the objective progression even after discontinuation of treatment.
2. In some circumstances, it may be difficult to distinguish residual disease from normal tissue. When the evaluation of complete response depends upon this determination, it is recommended that the residual lesion be investigated (fine needle aspirate/biopsy) before confirming the complete response status.

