14.0 CRITERIA FOR REMOVAL FROM STUDY

In the absence of serious toxicity or complications, all patients will receive at least one cycle of treatment. In the absence of treatment delays due to adverse event(s), treatment may continue until one of the following criteria applies:

- Disease recurrence/progression, defined as emergence of an unequivocal new tumor (site of metastasis) > 1 cm in size, clinical progression in non-measurable sites of disease, or unequivocal changes in size of the primary tumor.
- Development of an intercurrent medical condition or need for concomitant treatment that precludes further participation in the trial.
- Unacceptable toxicity or any adverse event that precludes further participation in the trial.
- The investigator removes the patient from the trial in the best interests of the patient.
- Patient death.
- Study completion or discontinuation.
- Patient withdraws consent to continued participation in the trial or is lost to follow-up.

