15.1 Sample size calculation

The phase I component of the study will consist of a traditional 3+3 dose escalation rule with 3 or 6 patients in each cohort, the process for dose escalation is outlined in section 4.1.

The median TTP of patients with advanced HCC treated with sorafenib therapy is 5.5 months. Using this as a benchmark, we will enroll 38 patients, which will allow us to differentiate between a median TTP of 5.5 months and 8.3 months with 80% power and a two-sided significance level of 10% assuming a 24-month accrual and a 12-month follow-up period. TTP will be calculated from initiation of therapy to disease progression (intention to treat) as outlined in section 13.0. Removal from study as outlined in section 14 will be a censored event.

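### No tumour scan is scheduled after removal from study and TTP is censored there, so removals for clinical deterioration are likely to lengthen the estimated TTP and other removals at least cost events

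*Combined protocol and SAP*

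**What the plan says.** All references are to the combined protocol and SAP, phase II component.

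- **Scanning.** Section 4.2.2: "CT or MRI will be performed every 6 weeks +/- 5 days following the initial 2-week studies until removal from study". Long-term follow-up in the same section is for overall survival only.
- **Exit.** Section 10.0 has a list headed "Investigations/tests at study exit due to disease progression or toxicity or following completion of the phase I component". It holds a venous duplex, history and physical, and laboratory tests, with no CT or MRI. The contact that continues is "History and physical examination (this will continue every 6 weeks for determination of secondary endpoint of overall survival").
- **Removal.** Section 14.0 includes "Unacceptable toxicity or any adverse event that precludes further participation in the trial", and also intercurrent conditions, the investigator's judgement and withdrawal of consent. Section 9.4 adds toxicity holds of more than 4 weeks.
- **Analysis.** Section 15.1: "TTP will be calculated from initiation of therapy to disease progression (intention to treat) as outlined in section 13.0", followed by "Removal from study as outlined in section 14 will be a censored event".
- **Progression after stopping.** Section 13.4, on "Patients with a global deterioration of health status requiring discontinuation of treatment without objective evidence of disease progression at that time", has these reported as symptomatic deterioration and adds: "Every effort should be made to document the objective progression even after discontinuation of treatment".
- **PFS.** Section 15.2 names Kaplan-Meier estimation but states no event or censoring rule for PFS.

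**The concern.** Scheduled measurement of the phase II primary endpoint ends when a patient leaves the study, although the patient is still seen every 6 weeks. A patient who leaves because of failing health, without a scan showing progression, is then censored. Kaplan-Meier estimation assumes that such a patient would have gone on to progress at the same rate as those who stayed. For deterioration in advanced hepatocellular carcinoma that is unlikely.

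The trial has one arm and is judged against a fixed 5.5 months, so there is no control arm in which the distortion could cancel. Where removal has nothing to do with progression risk, there is no distortion. Events are still lost, and the sample size makes no visible allowance for that.

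**Working it through.** **1. The plan's own figure.** Inputs from section 15.1: medians 5.5 and 8.3 months, 80% power, two-sided 10%, accrual 24 months, follow-up 12 months. No test is named. I assume exponential TTP, uniform accrual and a one-sample log-rank test.

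- λ1 = ln 2/8.3 = 0.0835 per month.
- Event probability p = 1 − [exp(−12λ1) − exp(−36λ1)]/(24λ1) = 0.8415.
- Events expected per patient at the benchmark hazard: e = p × 8.3/5.5 = 1.270.
- N = (1.645√e + 0.8416√p)²/(e − p)² = 37.6, that is 38. This gives about 32 events and 80.5% power.

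So 38 reproduces with nobody removed before progression. Other single-sample formulas give, for example, 36.8, 39.2 or 43.4, so the choice of test is an inference.

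**2. Removal unrelated to risk: loss of power.** Let f be the assumed share removed before progression. The removal hazard is g = λ1·f/(1 − f), and h = λ1 + g. Then p = (1 − f){1 − [exp(−12h) − exp(−36h)]/(24h)}, e = p × 8.3/5.5, and power = Φ{[√38(e − p) − 1.645√e]/√p}. At f = 30%: h = 0.1193, p = 0.645, e = 0.973, power 69.1%.

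| f | Events | Power |
|---|---|---|
| 0 | 32.0 | 80.5% |
| 10% | 29.7 | 77.5% |
| 20% | 27.2 | 73.7% |
| 30% | 24.5 | 69.1% |
| 40% | 21.6 | 63.4% |

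**3. Removal related to risk: bias.** Assume no drug benefit (true median 5.5 months), progression hazard λ before removal and kλ after it, and removal hazard rλ with r = f/(1 − f). True progression-free probability:

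S(t) = exp[−(1 + r)λt] + {r/(1 + r − k)}{exp(−kλt) − exp[−(1 + r)λt]}.

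Set S(5.5) = 0.5 and solve for x = 5.5λ. Kaplan-Meier with censoring at removal estimates exp(−λt), so the apparent median is 5.5 × 0.6931/x. At f = 30% and k = 2: 1.75·exp(−1.4286x) − 0.75·exp(−2x) = 0.5 gives x = 0.628 and a median of 6.07 months.

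| Apparent median (months) | f = 10% | 20% | 30% |
|---|---|---|---|
| k = 1 (unrelated) | 5.5 | 5.5 | 5.5 |
| k = 2 | 5.7 | 5.9 | 6.1 |
| k = 4 | 5.8 | 6.2 | 6.7 |
| Extreme case | 6.1 | 6.9 | 7.9 |

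In the extreme case every removal falls in the 6 weeks before the scan that would have shown progression. The hazard then falls by (1 − f) and the median is 5.5/(1 − f). The gain the trial aims for is 8.3 − 5.5 = 2.8 months.

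**4. Effect on the test.** In simulations with 38 patients, no benefit and a nominal one-sided 5% exponential test against 5.5 months, the chance of a false positive was:

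| Scenario | Censored at removal | Followed to progression |
|---|---|---|
| f = 30%, k = 1 | 4.2% | 4.4% |
| f = 20%, k = 2 | 7.8% | 1.9% |
| f = 30%, k = 4 | 23.9% | 1.4% |

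The figures in the last column for k = 2 and 4 are below 5% because that test is conservative when the hazard rises over time.

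**The case against.** Each of these counter-arguments limits the point.

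- **Section 13.4 asks for later progression to be documented.** This stands against any claim that progression after removal is never measured. But the sentence concerns global deterioration only, sets no scan or interval, and section 15.1 would still censor the patient at removal.
- **Stopping scans is consistent with censoring at removal.** True. The conflict is between that censoring, the intention-to-treat label beside it, and section 13.4.
- **Clinical progression in non-measurable sites, a section 14.0 criterion, can be progression under section 13.** Sections 13.1.4 and 13.3 allow it. A reader might count it among the unmeasured removals; the documents do not support that.
- **Upward bias is not shown for every removal.** Nothing in the documents says that patients leaving for toxicity, intercurrent illness or investigator decision progress sooner.
- **The extreme case invites too large a claim.** A reader might infer that 34% removal (1 − 5.5/8.3 = 0.337) would reproduce the 8.3-month target without benefit. That needs every removal to sit just before the progression scan. Counting no-effect trials whose observed median reaches 8.3 months is no better a guide. The protocol has no such decision rule, and the sixth 6-weekly scan falls at 36 weeks, or 8.28 months, so the count turns on a hair's breadth.
- **PFS.** A reader might infer that death is the only PFS event these patients can supply. With no stated rule, and with section 13.4 allowing later documentation, that cannot be said.
- **Section 14.0 lists progression itself as a removal reason.** Read literally, section 15.1 would censor its own endpoint. The preceding sentence defines TTP by progression under section 13, so this is unlikely to be meant, but the text should exclude it.

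**Conclusion.** The point holds as a gap between sections 4.2.2, 10.0, 13.4 and 15.1. No scan is scheduled or required after removal, and the TTP rule would set aside progression that section 13.4 asks sites to document. Censoring removals for clinical deterioration without objective progression is likely to inflate TTP. For other removals the direction is unknown. If they are unrelated to risk, the cost is power: from about 80% to 77–69% with 10–30% removed.

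On the assumptions above, the inflation runs from nothing, through 0.2–0.6 month (twice the hazard) and 0.3–1.2 months (four times), to 0.6–2.4 months only in the extreme case. Removal shares and hazard ratios are my assumptions; the documents supply neither. PFS has the same weakness, of a size that cannot be stated until its rule is written.

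**What to change.** Reconcile sections 4.2.2, 10.0, 13.4 and 15.1, and in 15.1 replace censoring at removal with these rules:

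1. Progression by Section 13 criteria is always an event, including when it is the reason for removal.
2. Progression by the same criteria documented after removal also counts as the TTP event. The source is CT or MRI done in routine care, collected at the 6-weekly visits that already continue after exit and read by RECIST.
3. Patients without documented progression are censored at their last evaluable scan.
4. Section 15.2 states the PFS event and censoring rule, using the same progression dates.

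Report sensitivity analyses that (a) censor at removal, (b) count removal for symptomatic deterioration as an event, and (c) censor at the start of new anticancer therapy.

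The cost is protocol wording plus collecting and reading scans done anyway. Routine scans after removal will be irregular, and some will follow other therapy; analyses (a) and (c) show how much that matters. Protocol-mandated scans at exit or after removal would give better data, but they are extra procedures for patients who have left treatment, and section 17.0 makes patients pay for most MRI. They are optional and the fix does not depend on them.

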5.0 THERAPEUTIC/DIAGNOSTIC AGENTS

5.1 Bavituximab

IND Number: 109134

Finished Product

Presentation and Composition

Bavituximab is supplied as a sterile, preservative-free solution with 10 mM acetate at pH 5.0 and diluted with 0.9% (w/v) saline (normal saline) to a final volume of 100 mL.

Storage

Bavituximab is stored at 2°C to 8°C. Once diluted, it should be stored at room temperature and used within 8 hours.

Availability and Accountability

Peregrine Pharmaceuticals, Inc in Tustin, CA will provide bavituximab. The pharmacist or designee must keep an accurate accounting of the number of investigational units received from Peregrine, dispensed to patients, and returned to Peregrine during and at the completion of the study. A detailed inventory must be completed for the study medication. The study medication must be dispensed only by an appropriately qualified person to patients in the study. The medication is to be used in accordance with the protocol in patients who are under the direct supervision of an investigator. All unused clinical study medications/treatments will be returned to Peregrine.

Administration

Bavituximab will be administered weekly. Prior to each bavituximab infusion, the patient must be pre-medicated with a steroid and an antihistamine to decrease the risk of an infusion reaction, 250 mg hydrocortisone IV and 50 mg diphenhydramine IV administered 30 minutes prior to infusion will be given.

Infusion preparation and administration are to be performed as follows:

1. Draw up the volume of a vial using a sterile syringe attached to an appropriate needle (a vented spike or other appropriate transfer device may be used). Fill treatment into a sterile glass bottle or plastic IV bag.
2. Using aseptic techniques, repeat procedure until the calculated volume has been put in to the container. Bring the final volume to 100 mL using 0.9% Sodium Chloride Injection, USP.
3. Administer through a low protein binding 0.2-micrometer in-line filter (placed as proximal to the patient as practical).
4. Affix the infusion line and prime it with infusate before starting the infusion. Infuse the solution intravenously over 90 (\pm 10) minutes. No reduction in infusion time will be permitted. Flush the line with normal saline after infusion.

